Background and Rationale:	Aspiration pneumonias still exhibit a significant morbidity and mortality ¹⁻⁶ and are accountable for a significant part of anaesthesia-related deaths. Various diseases and especially emergency situations correlate with prolonged gastric emptying and therefore with a higher risk of pulmonary aspiration. In clinical practice the decision to perform a Rapid Sequence Induction (RSI) is mostly based on clinical and anamnestic findings. Preoperative gastric sonography may provide an objective, validated, non-invasive, reliable, fast, and cost-efficient approach to assess aspiration risks in both elective and emergency patients. How this highly sensitive and specific tool may be best introduced and implemented in daily clinical practice or anaesthesiologic guidelines remains unclear. Structured educational programmes or training recommendations for this point-of-care ultrasound application rarely exist.
Objectives:	
 1. Establish preoperative gastric sonography before Rapid Sequence Induction (RSI) and patients with one or more aspiration risk factors scheduled for a advanced laryngeal mask or regional anaesthesia at the Kantonsspital Winterthur, Department of Anaesthesiology. 2. Validation of our structured training/education by comparing sonographic estimated and directly measured gastric content. 3. Emphasize the importance and effectiveness of this diagnostic tool to improve anaesthesiologic management.

Outcomes:	Primary Endpoint: - Correlation of sonographic estimated gastric volume with volume aspirated through a naso- or orogastric tube. Secondary Endpoints: - Performance over time, improvement of examination technique, critical number of examinations to achieve a high quality standard (>80% congruence for estimated and aspirated gastric volume in fluids). - Association of performance with experience, residents vs. attendings. - Number of patients classified as empty -> possible implications for management and induction - Number of patients with full stomach -> possible implications for management and induction - Time used for examinations, time used with growing experience. - estimated aspiration risk vs. sonographic gastric volume - Total number of pulmonary aspirations
Study design	A prospective observational study
Inclusion criteria:	
 • All elective in-hospital Rapid Sequence Inductions (RSI) and patients with one or more aspiration risk factors scheduled for a advanced laryngeal mask or regional anaesthesia with informed consent. • All emergency in-hospital RSI and patients with one or more aspiration risk factors scheduled for an advanced laryngeal mask or regional anaesthesia with informed consent graded as follows according to the Swiss Society for Anaesthesiology and Resuscitation (A-QUA): “Notfall 1-6h, nicht vital (dringlicher Eingriff)”, “Notfall 6-24h nicht vital (aufgeschobener dringlicher Eingriff)”
Exclusion criteria:	
 • Life threatening/ time critical emergency interventions, graded followingly according to the Swiss Society for Anaesthesiology and Resuscitation (A-QUA): “Notfall <1h, vital (sofortiger Eingriff notwendig)” • Known Pregnancy • Obstetric surgery • Underage (< 18 years) • Absence of informed consent (missing or inability to provide) • No anaesthetist with completed structural education in gastric sonography is available. • Contraindications for naso- or orogastric tubes or inability to correctly place such.
Intervention, Measurements and procedures:	Our study will be performed mainly in the induction rooms of our operating ward and occasionally inside the operating theatre. Standard care will be given to every patient at the usual location, with our usual equipment (anaesthetic machine, monitoring, medication and airway devices etc) and by our usual anaesthesiologic team members. Sonographic examination and determination of the gastric content will be executed on one of our standard ultrasound machines (Venue and LOQIC e from GE-Healthcare®) with a curved

	array low frequency (2-10 Hz) abdominal probe or portable ultrasound devices (IQ+ from Butterfly Network Inc. ®).
Control Intervention:	
Number of Participants with Rationale:	A total number of 2'718 general anaesthesia with Rapid Sequence Inductions (RSI) was undertaken at our institution in 2019. Thereof, 275 were children < 18 years of age. 204 Rapid Sequence Inductions were performed in category: "Notfall <1h, vital, sofortiger Eingriff notwendig" and therefore not includable. Therefore, expect to include around 1500 - 2200 patients in a one year period.
Study Duration:	Estimated duration of the project: 18 months Planned start: 01/2021 Planned project close: 06/2022
Study Schedule:	Project specific: 
 • Time period for participant recruitment: 12 months • Project start (FPFV): 01/2021 • Project end (LPLV): 12/2021
Investigators:	[name] (Sponsor), [name] (PI) Co-Investigators: [name], [name], [name] Sub-Investigators: All anaesthesia faculties and residents of the department of Anaesthesiology, Kantonsspital Winterthur after completion of our special training program in gastric sonography (see Chapter 8) All investigators are members of: Department of Anaesthesiology Kantonsspital Winterthur [name]
Study Centre:	This study will be conducted at the Department of Anaesthesiology at the Cantonal Hospital of Winterthur, a Swiss teaching hospital. In our department we care for a total of approximately 18'000 patients per year. The anaesthetic physician team consists of 25 qualified/staff anaesthetists and 29 trainee anaesthetists, all with basic knowledge of point-of-care-ultrasound (e.g. vascular access, peripheral nerve blocks). In the past several clinical studies including multi- as well as single-centre studies have been successfully conducted at our institution.
Statistical Considerations:	Collected Variables 
 • Patient Demographic: Age, sex, gender, height, weight, BMI, ASA Classification, patient history, concomitant medication, concomitant disease, intervention performed, anaesthetic risk class of the intervention, surgical department of the intervention, urgency of the intervention. • Sonographer Demographic: education level, years of anaesthesiologic experience, years of sonographic experience

	
 • risk factors for pulmonary aspiration • Last meal/ drink before surgery • Subjective estimated aspiration risk (graded by the responsible anaesthetist) • Sonography quality, reasons for poor quality • Sonographic quality of gastric content • Sonographic quantity of gastric content • Time for examination • Effective quantity of gastric content • Theoretical change in anaesthesiologic management • Reason for not performing gastric sonography 
Analyses
 
 • Institution overall success analysis • Interpersonal success analysis • Analysis of theoretical changes in anaesthesiologic management
GCP Statement:	
This study will be conducted in compliance with the study protocol, the current version of the Declaration of Helsinki, the ICH-GCP directive, the HFG and HFV as well as all other relevant national legal and regulatory requirements.

Study Schedule

	Expert and Resident Training in Sonography (11/2020 – 02/2021)	Screening (01/2021 – 12/2021) Prior to arrival at OR suite	Day of Surgery (01/2021 – 12/2021) = Day 1
Expert (study core group, faculties) Training	√		
Anaesthesia resident Training	√		
Training Participants Demographic and Experience Data	√		
Participant Information and Informed Consent		√	
Inclusion- and Exclusion Criteria		√	
Demographic Data		√	
Medical History / Concomitant Diseases / Concomitant Medication		√	
Sonography and Data Collection			√
Gastric Volume direct measurement			√
Serious Events			√

Table of Contents		Page
1	Abbreviations	8
2	Project Personal and Administration.....	9
3	Introduction	10
3.1	Background and Project Purpose	10
3.2	Categorisation	11
4	Project Objectives	12
4.1	Project Objectives	12
4.2	Project Outcomes.....	12
5	Project Description	13
5.1	Design	13
5.2	Number of Project Participants	13
5.3	Project Schedule	13
5.4	Risk-benefit considerations.....	13
6	Eligibility of the Project Site.....	14
7	Recruitment	15
7.1	Inclusion Criteria	15
7.2	Exclusion Criteria	16
7.3	Premature Withdrawal Criteria.....	16
8	Project Measures	17
8.1	Measures/procedures to collect health related personal data	17
9	Safety	19
9.1	Definition Serious Events.....	19
9.2	Assessment and Documentation of SEs	19
9.3	Reporting of SEs	19
9.4	Reporting of Safety and Protective Measures	20
10	Data - und Quality Management.....	21
11	Statistical Plan.....	22
11.1	Determination of Sample Size	22
11.2	Statistical Methods	22
12	Ethics	24
12.1	Independent Ethics Committee	24
12.2	Ethical Conduct of the Project.....	24
12.3	Participant Information and Informed Consent	24
13	Confidentiality and Data Protection.....	25
14	Funding and Support.....	25
15	Compensation	25
16	Insurance	25
17	Publication Policy	26
18	Signatures	27
19	References.....	28

1 Abbreviations

HFG	Humanforschungsgesetz
HFV	Humanforschungsverordnung (Ordinance on human research with exception of clinical trials/HRO)
HRO	Human Research Ordinance
ICH	International Conference on Harmonization
SE	Serious Event
RSI	Rapid Sequence Induction
POCUS	Point-of-care ultrasound
CSA	Cross sectional area
SGAR	Swiss Society for Anaesthesiology and Resuscitation

3.1 Background and Project Purpose

In 1946, Mendelson⁸ was first to recognize the potential danger of anaesthesia related pulmonary aspiration, defined as the presence of bilious secretion in the tracheobronchial tree, and to describe its detrimental consequences.¹ The presence of intestinal fluids in the respiratory system results in a chemical pneumonitis and may lead to acute hypoxemia or bronchospasm or end up in an aspiration pneumonia.⁹ Pulmonary aspiration is a relatively rare event, with an incidence ranging from 0.01 up to 0.8 % according to literature.^{1-5, 10} Despite its low incidence, aspiration pneumonias may still exhibit a substantial morbidity and mortality¹⁻⁶ and are accountable for a significant part of anaesthesia-related deaths.^{6,7}

The majority of the perioperative pulmonary aspirations occur shortly before or during laryngoscopy or throughout extubation.^{1,6} In emergency or critical care medicine the risk of pulmonary aspiration seems to be significantly increased.^{10,11} Further risk factors include gastrointestinal obstruction, recent food intake, lack of coordination of swallowing, obesity, ASA status, pregnancy, age, surgical procedure and other co-morbidities (insulin dependent diabetes, hepatobiliary- or renal dysfunction or cardiorespiratory diseases).^{1,4}

Accordingly, strategies to reduce the risk of aspiration have been developed and continuously updated. For elective surgeries American¹² and European¹³ guidelines recommend a minimum fasting time of 6 hours for solid and 2 hours for clear fluids. Recent guideline updates for paediatric patients resulted in a reduced fasting time for clear liquids of 1 hour prior to elective surgery, as prolonged fasting times had been identified as a negative predictor for adverse physiological response to surgery and reduced fasting intervals improved patient comfort and compliance.^{14,15}

For emergency surgeries in non-fasted patients or patients with increased risk of aspiration Rapid Sequence Induction (RSI) is broadly accepted and executed as a standard procedure.¹⁶ However, RSI is accompanied by significant risks concerning haemodynamic stability and oxygenation in case intubation and mask ventilation fails.^{17,18} Most importantly, evidence of a decreased incidence of pulmonary aspiration after Rapid Sequence Induction (RSI) is still lacking.¹⁹

Fast, simple, non-invasive and cost-effective strategies to assess a patient's risk of aspiration and adapt the anaesthetic strategy accordingly are greatly needed. Here, point-of-care sonography (POCUS) with preoperative assessment of the gastric content allows a fundamentally new approach for patients at risk of gastric regurgitation by adding an objective tool - not relying on patient history alone.^{11, 20} Gastric sonography seems to be highly sensitive and specific.^{21, 22} Recent studies, especially highlighted the accuracy for the qualitative²³⁻²⁷ and quantitative assessment^{22, 25, 26, 28} of the gastric content. For the quantitative analysis of gastric content, present data suggest a strong numerical correlation between an ultrasound-determined antral cross-sectional area (CSA) and the total volume of gastric fluid.^{11, 28} A residual gastric volume of more than 1.5 ml/kg for fluid content has been identified to signal an increased risk for gastrointestinal regurgitation and for pulmonary aspiration and this cut-off value has been utilized in various studies.^{20, 29} Consequently, there is an increasing consensus in scientific literature that preoperative gastric sonography should be performed in all emergency situations and in elective interventions in patients with increased probability of presenting with a full stomach and accordingly an increased risk of pulmonary aspiration.³⁰⁻³⁴ The routine application of gastric POCUS for elective surgery with fasted patients without risk factors is still controversial¹¹ although Van de Putte et al.³⁵ discovered a relevant percentage of full-stomachs in patients without risk factors of delayed emptying of the stomach.

In summary, preoperative gastric sonography may provide a validated, reliable, fast, and cost-efficient approach to assess aspiration risks in both elective and emergency patients. Practiced sonographers are able to perform point-of-care gastric sonography in few minutes^{11, 27}, thus severe delay in daily clinical practice should not be expected. Nevertheless, how this highly sensitive and specific tool should be best established in daily clinical practice is further on unclear. There is no existing structural education/training for this specific point-of-care ultrasound application. Arzola et al. suggest a minimum of 30 ultrasounds an acceptable quality level, but evidence is scarce.³⁶

The aim of this investigation is to validate our structural training and proof the importance and effectiveness of this diagnostic tool to lay ground for improvement of anaesthesiologic management and presumably patient safety in patients with an increased risk of a pulmonary aspiration.

3.2 Categorisation

Category A: collection of health related personal data is associated with minimal risk and burdens only.

Gastric sonography is a very low risk examination. No ionizing radiation is used. Theoretical complications including sensation of local pressure or pain, regional exanthema or allergic reactions to ultrasonic gel will at most be very minor. The complete examination takes approximately five minutes accordingly anaesthesiologic and surgical procedures will not be significantly delayed. Patients and interventions where even a minimal delay may provide a potential health risk are not included in this study.

4 Project Objectives

4.1 Project Objectives

Primary objectives:

- Establish preoperative gastric sonography in patients with risk factors for pulmonary aspiration at the Kantonsspital Winterthur, Department of Anaesthesiology through a structured training/education - validated by comparing sonographic estimated and directly measured gastric content.

Secondary objectives:

- Identify possible confounders and variables in individual training.
- Emphasize the importance and effectiveness of this diagnostic tool to improve anaesthesiologic management and possibly patient safety by identifying the number of possible interventions and changes in anaesthesiologic management and correlation of estimated and actual gastric volume in fluids.

4.2 Project Outcomes

Primary Endpoint:

- Correlation of sonographic estimated gastric volume with volume aspirated through a naso- or oro-gastric tube, that was placed by routine.

Secondary Endpoints:

- Performance over time, improvement of examination technique, critical number of examinations to achieve a high quality standard (>80% congruence for estimated and aspirated gastric volume in fluids).
- Association of performance with experience, residents vs. attendings.
- Number of patients classified as empty -> possible implications for management and induction.
- Number of patients with full stomach -> possible implications for management and induction.
- Time used for examinations, time used with growing experience.
- Estimated aspiration risk vs. sonographic gastric volume.
- Total number of pulmonary aspirations.

5 Project Description

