Tutors/experts are all expert sonographers on different modalities. They will receive a preceding 240 minutes training, consisting of a 60 minutes theoretic introduction and a 60 minutes course by a radiologist and abdominal sonography expert, certified by the Swiss Society for Sonography. The remaining time will consist of individual exercise on healthy volunteers and at least 10 trial sonographies with gastric volume calculation under supervision of another member of the tutor group.

Our study will be performed mainly in the induction rooms of our operating unit and occasionally inside the operating theatre. Standard care will be given to every patient at the usual location, with our usual equipment (anaesthetic machine, monitoring, medication and airway devices and so on) and by our usual anaesthesiologic team members. Sonographic examination and determination of the gastric content will be executed on one of our standard ultrasound machines (Venue and LOQIC e from GE-Healthcare®) with a curved array low frequency (2-10 Hz) abdominal probe or our portable ultrasound devices (IQ+ from Butterfly Network Inc.®).

Before performing the sonographic examination, the responsible anaesthesiologist will be asked to rate the estimated risk of pulmonary aspiration, based on personal impression, patient history and clinical finding. All anaesthetists are advised to perform the examination only if they could guarantee privacy before they expose patient abdomen for the examination. Primarily, a qualitative assessment of the gastric content should be performed in supine and right-lateral decubitus (RLD) position. In low volume states a right-lateral decubitus position (RLD) has the advantage of a gravitational shift to the antrum. That is why we plan to perform the examination in both positions. If RLD position is not possible due to patient factors a half sitting position can be tried. Gastric content will be classified into empty, fluid, solid or mixed. Examiners will be asked to classify sonographic conditions into poor, medium or good and provide a reason in case of limited conditions. If fluid gastric content is detected an estimation of the quantity should be performed as follows.

After identification, CSA will be measured and gastric content is estimated by implementation of the formula described by Perlas et al: ^{20, 28}

$$\text{Gastric Volume (ml)} = 27.0 + 14.6 \times \text{right-lateral CSA (cm}^2\text{)} - 1.28 \times \text{age (years)}.$$

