This model is based on gastroscopic fluid assessment and highly validated by several publications. ²⁸

After placement of the routine naso- or orogastric tube, which is a standard procedure for both RSIs and advanced laryngeal masks at our institution - we compare the calculated and effective suctioned volume of the gastric content and analyse the difference and quality of the sonographic measurement. In some patients a gastric tube is contraindicated or not possible to place correctly. In this case an exclusion of the study is mandatory according to our exclusion criteria. Patients planned for an intervention in a regional anaesthesia will not receive a gastric tube.

In exceptional cases the responsible anaesthesiologist is allowed to upgrade patients from an advanced laryngeal mask to an RSI after ultrasound performance to ensure patient safety. Downgrading from RSI to advanced laryngeal masks on base of the ultrasound results is not allowed.

All data concerning the sonography will be noted in a password protected Excel sheet only available to institute members by the responsible anaesthesiologist performing the examination. Background patient data including demographic data are collected during the structured preoperative anaesthesiologic assessment according to in house standard procedures and data management. Data will be coded and condensed in a password-protected Excel File, only accessible to study personnel. A patient identification log will be kept in a locked archive for data verification processes only. To guarantee seamless traceability we will create a immutable PDF file after all relevant changes or at least once per month and store it in a separate study folder only accessible to study personnel. An additional hard copy will be created and printed once per month and stored in a locker in our administrative office.

9 Safety

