11.2 Statistical Methods

Primary Endpoint:

- Correlation of sonographic estimated gastric volume with volume aspirated through a naso- or orogastric tube.

Secondary Endpoints:

- Performance over time (improvement of examination technique, critical number of examinations).
- Association of performance with experience, residents vs. attendings.
- Number of patients classified as empty -> possible implications for management and induction.
- Number of patients with full stomach -> possible implications for management and induction.
- Time used for examinations, time used with growing experience.
- estimated aspiration risk vs. sonographic gastric volume.
- Total number of pulmonary aspirations.

Collected Variables:

- Patient Demographic: Age, sex, gender, height, weight, BMI, ASA Classification, patient history, concomitant medication, concomitant disease, intervention performed, anaesthetic risk class of the intervention, surgical department of the intervention, urgency of the intervention.
- Sonographer Demographic: education level, years of anaesthesiologic experience, years of sonographic experience.
- RSI Indication.
- Last meal/ drink before surgery.
- Subjective estimated aspiration risk (graded by the responsible anaesthetist).
- Sonography quality, reasons for poor quality.

- Sonographic quality of gastric content.
- Sonographic quantity of gastric content.
- Time for examination.
- Effective quantity of gastric content.
- Theoretical change in anaesthesiologic management.
- Reason for not performing gastric sonography.

Analysis:

- Demographic Analysis.
- Institution overall success analysis.
- Interpersonal success analysis with logistic regression and cumulative sum learning curves.
- Analysis of possible changes in anaesthesiologic management.

12 Ethics

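### The primary endpoint is a correlation, which cannot show whether the volume estimates are right, although the stated objective is to validate them against measured volume

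*Protocol*

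**What the plan says.** Section 4.2 of the protocol defines the primary endpoint as "Correlation of sonographic estimated gastric volume with volume aspirated through a naso- or oro-gastric tube, that was placed by routine". The synopsis (Outcomes) and section 11.2 repeat it; the latter reads "Correlation of sonographic estimated gastric volume with volume aspirated through a naso- or orogastric tube". No type of coefficient and no target value is given.

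The objectives are worded differently. Objective 2 in the synopsis is "Validation of our structured training/education by comparing sonographic estimated and directly measured gastric content". The primary objective in 4.1 is to establish gastric sonography through a structured training, "validated by comparing sonographic estimated and directly measured gastric content".

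Two other places come close to agreement:

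- Section 8.1, after describing the gastric tube, says "we compare the calculated and effective suctioned volume of the gastric content and analyse the difference and quality of the sonographic measurement".
- A secondary endpoint in 4.2 sets a quality standard of ">80% congruence for estimated and aspirated gastric volume in fluids", without saying what counts as congruent.

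The analyses listed in 11.2 are a demographic analysis, an overall success analysis, an interpersonal analysis with logistic regression and cumulative sum curves, and an analysis of possible management changes. None names a mean difference, limits of agreement or an accuracy limit for the primary endpoint.

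**The concern.** Whether trained sonographers obtain the right volume is a question of agreement between two measurements on one scale. A correlation answers another question: whether patients with larger aspirated volumes also tend to have larger estimates. Two properties make it unsuitable as the sole primary measure here.

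- **It ignores systematic error.** Habitual over- or under-tracing of the antrum is a fault that training should remove, and it can leave the coefficient untouched.
- **It depends on case mix.** The same measurement error gives a low coefficient in patients with similar volumes and a high one in patients with widely spread volumes.

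Systematic error matters because section 3.1 ties the estimate to an absolute value: "A residual gastric volume of more than 1.5 ml/kg for fluid content has been identified" as signalling increased risk. Biased estimates move patients across that value. They would also distort the secondary counts of full and empty stomachs, as far as those counts rest on volume. A low correlation could still warn of poor performance, but a high one could be reported as successful validation while the estimates are consistently wrong.

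**Working it through.** **1. The plan's own figure.** Section 11.1 takes 30 residents and 20 attendings with 30 to 40 examinations each: 50 × 30 = 1500 and 50 × 40 = 2000. This reproduces the stated 1500 to 2000. The number does not come from an expected correlation, so changing the endpoint does not disturb this derivation.

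**2. What follows from the formula alone.** Section 8.1 says "After identification, CSA will be measured and gastric content is estimated by implementation of the formula":

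volume (ml) = 27.0 + 14.6 × CSA (cm²) − 1.28 × age (years).

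- CSA traced 1 cm² too large: +14.6 × 1 = +14.6 ml on every estimate.
- CSA traced 2 cm² too large: +14.6 × 2 = +29.2 ml on every estimate.

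For an estimate E and an aspirated volume A, corr(a + bE, A) = corr(E, A) for any b > 0. The coefficient is therefore identical in both cases. This needs no assumption about patients.

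**3. Illustration under assumptions.** The protocol gives none of these inputs: age normal with mean 60 and SD 15, cut to 18–95; true volume gamma with mean 75 ml and SD 60 ml; random CSA error SD 1.5 cm²; complete suction; formula exact for each patient; weight 75 kg, so 1.5 × 75 = 112.5 ml. True CSA is (volume − 27.0 + 1.28 × age) / 14.6. The true share above 112.5 ml is 21.1%.

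| Tracing of CSA | r | Mean difference (ml) | 95% limits (ml) | Estimates above 112.5 ml |
|---|---|---|---|---|
| Accurate | 0.94 | 0 | −43 to +43 | 22.5% |
| +1 cm² | 0.94 | +14.6 | −28 to +58 | 28.7% |
| +2 cm² | 0.94 | +29.2 | −14 to +72 | 36.3% |
| 10% too large | 0.94–0.95 | about +12.5 | not tabulated | 28.5–28.8% |
| 30% too large | 0.94–0.96 | about +37.4 | −19 to +94, or −30 to +104 | 40.6–41.3% |

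Ranges show random error not scaled, or scaled, with the area. Hand check of the 30% row: mean CSA = (75 − 27.0 + 1.28 × 60) / 14.6 = 124.8 / 14.6 = 8.55 cm², and 0.30 × 8.55 × 14.6 = 37.4 ml.

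**4. Sensitivity.** With volume SD 40–80 ml, CSA error SD 1.0–2.5 cm² and unscaled random error, r is 0.74–0.98 for accurate tracing and 0.82–0.99 at 30% over-tracing. In each combination the biased r is at least as high as the accurate one, and the mean difference is +37 to +38 ml throughout. If random error scales with the area, r falls very slightly (for example 0.937 against 0.939).

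**5. A second set of assumptions.** With aspirated volume gamma with mean 80 ml, error SD 25 ml and 1500 patients, r is 0.908 without bias and also after shifts of +50 or −50 ml. The observed mean differences are −0.3, +49.7 and −50.3 ml. The concordance coefficient falls from 0.904 to 0.659 and 0.655. Misclassification at 105 ml (1.5 ml/kg at an assumed 70 kg) goes from 11.1% to 35.3% and 17.3%.

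**6. Dependence on case mix.** With a fixed error SD of 30 ml, r = SD / √(SD² + 30²), where SD is that of the true volumes. At SD 20 ml this is 20 / √1300 = 0.55. At SD 100 ml it is 100 / √10900 = 0.96.

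**7. Error in the reference.** If suction recovers an assumed 90% or 80% of a mean 75 ml, unbiased scans show an apparent mean difference of 0.10 × 75 = +7.5 ml or 0.20 × 75 = +15 ml.

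**The case against.** The strongest reply is that agreement is already planned. Section 8.1 promises to analyse the difference, 4.2 has the congruence standard, and an overall success analysis needs some criterion of closeness. If congruence meant within 20 ml, the share of congruent scans in the illustration would fall from about 64% to about 26% at 30% over-tracing, so that endpoint would expose the error. This stands in part: the protocol does not neglect differences. But congruence is undefined and secondary, and the difference analysis is not carried into 4.2 or 11.2. An analysis plan could add differences beside r, but the headline result would remain the correlation fixed in three places.

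The wording is also loose. The main verb of the primary objective is to establish sonography, and a secondary objective in 4.1 itself speaks of correlation. Validation by comparison is nevertheless the test the primary objective names.

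The simulated sizes rest on assumptions. Adding an assumed individual formula error with SD 40 ml lowers the accurate r from 0.94 to about 0.80. That changes the level of r, not its blindness to a shift.

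Aspirated volume is an imperfect reference, and a limit on the mean difference could penalise good training or let opposite errors cancel. This stands as a limitation and is a reason to report both measures. It does not make correlation sensitive to bias.

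Finally, this is a single-cohort observational study with no test attached to r, and no data would be lost. That makes the repair cheap; the central claim would still rest on an unsuitable measure.

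**Conclusion.** The concern holds and should be fixed before analysis, because it affects the primary endpoint and the main claim of the study. The endpoint as stated cannot answer the primary objective: a high correlation is compatible with estimates that are consistently too high or too low, and no criterion says when the training counts as validated.

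The blindness to shifts and to scaling of the estimates is a mathematical fact. The 14.6 ml per cm² comes from the protocol's formula. All other sizes, including the mean error of about 37 ml with r still 0.94 to 0.96, and 41% of scans above the 1.5 ml/kg value against a true 21%, rest on the assumed ages, volumes, errors and weight. They are illustrations, not forecasts for this hospital.

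**What to change.** In the synopsis, 4.2 and 11.2, replace the primary endpoint with wording such as: agreement between sonographically estimated and aspirated gastric volume in patients with fluid gastric content and a gastric tube, expressed as the mean difference (estimated minus aspirated, in ml) with 95% limits of agreement and 95% confidence intervals that allow for clustering by sonographer, judged against an acceptable limit fixed before analysis. The sponsor sets and justifies that limit.

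In addition:

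- Define the congruence standard on the same scale, for example as the share of scans within that limit.
- Report classification at the 1.5 ml/kg value cited in 3.1 as a supporting result.
- Keep the correlation as a descriptive result beside the differences.
- State as a limitation that incomplete suction appears as over-estimation, and that formula error also enters the difference.

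The cost is a change of wording in three places and one prespecified limit. No new data are needed. The headline may look less favourable than a high r, and part of any mean difference will not be operator error.
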